#### **10.9.8.5.5. Visit C5 – 3-Month Follow-Up Visit (84-98 Days After Visit C1)**

- Record nonstudy vaccinations as described in [Section 10.9.6.9](#).
- Record details of any of the prohibited medications specified in [Section 10.9.6.9.1](#) received by the participant if required for his or her clinical care.
- Collect a blood sample (approximately 10 mL for participants 12 through 17 years of age at the time of consent, and approximately 20 mL for participants  $\geq 18$  years of age) for immunogenicity testing, unless advised otherwise by Pfizer.
- Record SAEs (and any AEs occurring within 48 hours of blood draw or nasal swab collection) as described in [Section 8.4](#).
- Remind the participant or his/her parent(s)/legal guardian to contact the site staff or investigator if a medically attended event (eg, doctor's visit, emergency room visit) or hospitalization occurs.
- Ask the participant or his/her parent(s)/legal guardian to contact the site staff or investigator (this could be via the COVID-19 illness e-diary) immediately if the participant experiences any symptoms as detailed in [Section 10.9.8.5.8](#).

- Ensure that the participant has a self-swab kit in case of COVID-19 symptoms and provide instructions on self-collection of nasal swabs.
- Schedule an appointment for the participant to return for the next study visit.
- Complete the source documents.
- The investigator or an authorized designee completes the CRFs.

#### **10.9.8.5.6. Visit C6 – 6-Month Follow-Up Visit (175-189 Days After Visit C1)**

- Record nonstudy vaccinations as described in [Section 10.9.6.9](#).
- Record details of any of the prohibited medications specified in [Section 10.9.6.9.1](#) received by the participant if required for his or her clinical care.
- Collect a blood sample (approximately 10 mL for participants 12 through 17 years of age at the time of consent, and approximately 20 mL for participants  $\geq 18$  years of age) for immunogenicity testing, unless advised otherwise by Pfizer.
- Cohort 2 and Cohort 3: If the participant is part of the group for description of cell-mediated immune response (select sites only;  $\geq 18$  years of age only), collect a blood sample (approximately 130 mL) for PBMC isolation.
- Record AESIs and SAEs (and any AEs occurring within 48 hours of blood draw or nasal swab collection) as described in [Section 8.4](#).
- Collect the participant's e-diary provisioned device or assist the participant or his/her parent(s)/legal guardian to remove the study application from his or her own personal device.
- Complete the source documents.
- The investigator or an authorized designee completes the CRFs.

#### **10.9.8.5.7. Unscheduled Visit for a Grade 3 or Suspected Grade 4 Reaction**

If a Grade 3 local reaction ([Section 8.3.5.2](#)), systemic event ([Section 8.3.5.3](#)), or fever ([Section 8.3.5.4](#)) is reported in the e-diary, a telephone contact should occur to ascertain further details and determine whether a site visit is clinically indicated.

This includes:

- redness at the injection site measuring  $>20$  measuring device units ( $>10.0$  cm),
- swelling at the injection site measuring  $>20$  measuring device units ( $>10.0$  cm),

- severe injection site pain,
- fever  $\geq 39.0^{\circ}\text{C}$  ( $\geq 102.1^{\circ}\text{F}$ ),
- any severe systemic event.

If a suspected Grade 4 local reaction ([Section 8.3.5.2](#)), systemic event ([Section 8.3.5.3](#)), or fever  $>40.0^{\circ}\text{C}$  ( $>104.0^{\circ}\text{F}$ ) ([Section 8.3.5.4](#)) is reported in the reactogenicity e-diary, a telephone contact or site visit should occur to confirm whether the event meets the criteria for Grade 4.

A site visit must be scheduled as soon as possible to assess the participant unless:

- The participant is unable to attend the unscheduled visit, or
- The local reaction/systemic event is no longer present at the time of the telephone contact, or
- The participant or his/her parent(s)/legal guardian recorded an incorrect value in the reactogenicity e-diary (confirmation of a reactogenicity e-diary data entry error), or
- The investigator or authorized designee determined that the visit was not required, or
- The investigator or authorized designee confirmed severe reactogenicity assessment via medical records and/or telehealth assessment.

This telephone contact will be recorded in the participant's source documentation and the CRF.

If the participant is unable to attend the unscheduled visit, or the PI or authorized designee determined that it was not needed, any ongoing local reactions/systemic events must be assessed at the next study visit.

#### **10.9.8.5.8. COVID-19 and MIS-C Surveillance**

If a participant experiences any of the following (irrespective of perceived etiology or clinical significance), the participant or his/her parent(s)/legal guardian is instructed to contact the site immediately. If confirmed to be a potential COVID-19 illness, the site should schedule and conduct either an in-person or telehealth visit as soon as possible, optimally within 3 days after symptom onset (and at the latest 4 days after symptom resolution). Refer to [Section 10.9.8.2.1](#) for more details on COVID-19 and MIS-C surveillance.

- A diagnosis of COVID-19;
- Fever;
- New or increased cough;

- New or increased shortness of breath;
- Chills;
- New or increased muscle pain;
- New loss of taste/smell;
- Sore throat;
- Diarrhea;
- Vomiting.

Note that:

- The CDC list of COVID-19 symptoms can be found at: <https://www.cdc.gov/coronavirus/2019-ncov/symptoms-testing/symptoms.html>. The additional symptoms listed by the CDC (ie, those not listed in the above protocol-defined list) should not trigger a potential COVID-19 illness visit unless, in the opinion of the PI, deemed necessary.
- If new symptoms are reported within 4 days after resolution of all previous symptoms, they will be considered to be part of a single illness and a second illness visit is not required.
- Surveillance of potential COVID-19 symptoms should continue even if a participant has a positive SARS-CoV-2 test earlier in the study.

During the 7 days following the vaccination, potential COVID-19/MIS-C symptoms that overlap with specific systemic events (ie, fever, chills, new or increased muscle pain, diarrhea, vomiting) should not trigger a potential COVID-19 illness visit unless, in the investigator's opinion, the clinical picture is more indicative of a possible COVID-19 illness than vaccine reactogenicity. If, in the investigator's opinion, the symptoms are considered more likely to be vaccine reactogenicity, but a participant is required to demonstrate that he or she is SARS-CoV-2–negative, a local SARS-CoV-2 test may be performed. If the test result is positive, the symptoms should be recorded as a potential COVID-19 illness; if not, the symptoms that overlap with systemic events should be recorded in the reactogenicity e-diary or as AEs, if not captured in the reactogenicity e-diary.

The participant or his/her parent(s)/legal guardian is also instructed to contact the site immediately should the participant receive a positive SARS-CoV-2 test (NAAT or rapid antigen) result that is not accompanied by any symptoms. A potential COVID-19 visit is **not** required in this instance, but details of the positive test should be recorded in the designated CRF.

The participant or his/her parent(s)/legal guardian may utilize a COVID-19 illness e-diary through an application (see [Section 10.9.8.3.4](#)) installed on a provisioned device or on the participant's or his/her parent(s)/legal guardian's own personal device to prompt him/her to report a diagnosis of COVID-19 or any symptoms of COVID-19. Note that this does not substitute for a participant's routine medical care. Therefore, the participant or his/her parent(s)/legal guardian should be encouraged to seek care, if appropriate, from the participant's usual provider.

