#### **8.4.1.2. Recording Nonserious AEs and SAEs on the CRF**

All nonserious AEs and SAEs occurring in a participant during the active collection period, which begins after obtaining informed consent as described in [Section 8.4.1](#), will be recorded on the AE section of the CRF.

The investigator is to record on the CRF all directly observed and all spontaneously reported AEs and SAEs reported by the participant.

As part of ongoing safety reviews conducted by the sponsor, any nonserious AE that is determined by the sponsor to be serious will be reported by the sponsor as an SAE. To assist in the determination of case seriousness, further information may be requested from the investigator to provide clarity and understanding of the event in the context of the clinical study.

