3.1.1.2. Systemic Events

The systemic events assessed and recorded in the e-diary are fatigue/tiredness, headache, chills, vomiting, diarrhea, new or worsened muscle pain, and new or worsened joint pain within 7 days after the study vaccination. The e-diary entries from the participant and unplanned clinical assessments within 7 days after vaccination will be the primary data source for these events. In addition, any AEs recorded on the AE CRF that are considered systemic events starting within 7 days after vaccination will be consolidated with e-diary data and included in the reactogenicity report. The derivations for systemic events will be handled similar to the way local reactions are handled for presence of the event, severity level, duration, and onset day (see [Section 3.1.1.1](#)).

The symptoms will be assessed by the participant as absent, mild, moderate, or severe according to the grading scale in Table 8 and recorded in the e-diary. For events recorded in the AE CRF that are considered systemic events and consolidated with e-diary data, the severity will be based on the AE intensity grade recorded in the CRF.

If a Grade 3 systemic event is reported in the reactogenicity e-diary, a telephone contact should occur to ascertain further details and determine whether a site visit is clinically indicated. Only an investigator or medically qualified person is able to classify a participant's systemic event as Grade 4. If a participant experiences a confirmed Grade 4 systemic event, the investigator must immediately notify Pfizer and report it in the designated CRF as Grade 4. A Grade 4 systemic event will also be collected as an AE on the CRF. The event will be graded using the AE intensity grading scale,

Table 8. Systemic Event Grading Scale

	Mild (Grade 1)	Moderate (Grade 2)	Severe (Grade 3)	Potentially Life-Threatening (Grade 4)^a
Vomiting	1-2 times in 24 hours	>2 times in 24 hours	Requires IV hydration	Emergency room visit or hospitalization for hypotensive shock
Diarrhea	2 to 3 loose stools in 24 hours	4 to 5 loose stools in 24 hours	6 or more loose stools in 24 hours	Emergency room visit or hospitalization for severe diarrhea
Headache	Does not interfere with activity	Some interference with activity	Prevents daily routine activity	Emergency room visit or hospitalization for severe headache

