2.2. Study Objectives, Endpoints, and Estimands

The estimands corresponding to each primary and/or exploratory objective are described in Table 2.

The safety primary objective evaluations are based on the safety population. In general, completely missing reactogenicity data (ie, all 7 days of e-diary collection were missing and no reactogenicity events were reported on the participant-reported reactogenicity CRF) will not be imputed. For the partially missing reactogenicity data (ie, 1-6 days of reactogenicity data are available), it is assumed that no reactions or events were experienced on the missing days. Missing AE start dates will be imputed according to Pfizer safety rules ([Section 5.3](#)).

The estimands to evaluate the immunogenicity objectives are based on the evaluable immunogenicity population (see [Section 4](#) for definition). These estimands estimate the vaccine effect in the hypothetical setting where participants follow the study schedule and protocol requirements as directed. Missing antibody results will not be imputed. Immunogenicity results that are below the LLOQ will be set to $0.5 \times \text{LLOQ}$ in the analysis. This may be adjusted once additional data on the assay characteristics become available.

Table 2. List of Primary and Exploratory Objectives, Estimands, and Endpoints

Objectives	Estimands	Endpoints
Primary:	Primary:	Primary:
Safety		
Cohort 1 and Cohort 2 combined: To describe the safety and tolerability profile of BNT162b2 (Omi JN.1) 30 µg in participants ≥12 years of age.	In participants receiving 1 dose of study intervention, the percentage of participants reporting: 
 Local reactions for up to 7 days following the study vaccination Systemic events for up to 7 days following the study vaccination AEs from the study vaccination through 1 month after the study vaccination SAEs from the study vaccination through 6 months after the study vaccination 	
 Local reactions (pain at the injection site, redness, and swelling) Systemic events (fever, fatigue, headache, chills, vomiting, diarrhea, new or worsened muscle pain, and new or worsened joint pain) AEs SAEs

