If a Grade 3 local reaction is reported in the reactogenicity e-diary, a telephone contact should occur to ascertain further details and determine whether a site visit is clinically indicated. Only an investigator or medically qualified person is able to classify a participant’s local reaction as Grade 4, after clinical evaluation of the participant or documentation from another medically qualified source (eg, emergency room or hospital record) or telephone contact with the participant. If a participant experiences a confirmed Grade 4 local reaction, the investigator must immediately notify Pfizer. A Grade 4 reaction will be collected on the CRF.

Table 7. Local Reaction Grading Scale

	Mild (Grade 1)	Moderate (Grade 2)	Severe (Grade 3)	Potentially Life-Threatening (Grade 4)^a
Pain at the injection site	Does not interfere with activity	Interferes with activity	Prevents daily activity	Emergency room visit or hospitalization for severe pain
Redness	>2.0 cm to 5.0 cm (5 to 10 measuring device units)	>5.0 cm to 10.0 cm (11 to 20 measuring device units)	>10 cm (≥21 measuring device units)	Necrosis or exfoliative dermatitis
Swelling	>2.0 cm to 5.0 cm (5 to 10 measuring device units)	>5.0 cm to 10.0 cm (11 to 20 measuring device units)	>10 cm (≥21 measuring device units)	Necrosis

a. Only an investigator or medically qualified person is able to classify a reaction as Grade 4.

For each local reaction reported after the study vaccination, the maximum severity grade will be derived for the e-diary collection period (Day 1 through Day 7, where Day 1 is the day of the study vaccination) as follows:

Maximum severity grade = highest grade (maximum severity) within 7 days after administration (Day 1 through Day 7) among severity grades reported for that local reaction.

If a local reaction is captured in more than 1 data source, eg, the e-diary and the participant-reported reactogenicity CRF at unplanned assessments, the highest grade (maximum severity) across all sources will be used in the summary.

Duration (First to Last Day Reported)

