3.1.1.2. Systemic Events

The systemic events assessed and recorded in the e-diary and/or CRF are fatigue/tiredness, headache, chills, vomiting, diarrhea, new or worsened muscle pain, and new or worsened joint pain within 7 days after the study vaccination. The derivations for systemic events will be handled similar to the way local reactions are handled for presence of the event, severity level, duration, and onset day (see [Section 3.1.1.1](#)).

The symptoms will be assessed by the participant as absent, mild, moderate, or severe according to the grading scale in Table 8.

If a Grade 3 systemic event is reported in the reactogenicity e-diary, a telephone contact should occur to ascertain further details and determine whether a site visit is clinically indicated. Only an investigator or medically qualified person is able to classify a participant's systemic events as Grade 4 after clinical evaluation of the participant or documentation from another medically qualified source (eg, emergency room or hospital record) or telephone contact with the participant. If a participant experiences a confirmed Grade 4 systemic event, the investigator must immediately notify Pfizer. A Grade 4 systemic event will be collected on the CRF.

Table 8. Systemic Event Grading Scale

	Mild (Grade 1)	Moderate (Grade 2)	Severe (Grade 3)	Potentially Life-Threatening (Grade 4)^a
Vomiting	1-2 times in 24 hours	>2 times in 24 hours	Requires IV hydration	Emergency room visit or hospitalization for hypotensive shock
Diarrhea	2 to 3 loose stools in 24 hours	4 to 5 loose stools in 24 hours	6 or more loose stools in 24 hours	Emergency room visit or hospitalization for severe diarrhea
Headache	Does not interfere with activity	Some interference with activity	Prevents daily routine activity	Emergency room visit or hospitalization for severe headache
Fatigue/tiredness	Does not interfere with activity	Some interference with activity	Prevents daily routine activity	Emergency room visit or hospitalization for severe fatigue
Chills	Does not interfere with activity	Some interference with activity	Prevents daily routine activity	Emergency room visit or hospitalization for severe chills
New or worsened muscle pain	Does not interfere with activity	Some interference with activity	Prevents daily routine activity	Emergency room visit or hospitalization for severe new or worsened muscle pain

Table 8. Systemic Event Grading Scale

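### Substudy C: the protocol sends some diary-missed Day 1–7 systemic symptoms to the AE page, and the Substudy C SAP has no rule bringing them into the systemic-event endpoint

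*Protocol*

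**What the plan says.** The Substudy C surveillance text (protocol 10.9.8.5.8) names five symptoms that overlap with the prespecified systemic events: fever, chills, muscle pain, diarrhea and vomiting. It deals with their appearance in the first 7 days when the investigator thinks the vaccine the better explanation and a local test is not positive. In that case "the symptoms that overlap with systemic events should be recorded in the reactogenicity e-diary or as AEs, if not captured in the reactogenicity e-diary". Protocol 8.4.1.2 settles where an AE is entered: AEs in the active collection period "will be recorded on the AE section of the CRF".

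The Substudy C SAP, section 3.1.1.2, gives the sources of the endpoint as follows: "The systemic events assessed and recorded in the e-diary and/or CRF are fatigue/tiredness, headache, chills, vomiting, diarrhea" (muscle and joint pain complete the list). It borrows its derivations from section 3.1.1.1, where the rule for an event found in more than one place reads "eg, the e-diary and the participant-reported reactogenicity CRF at unplanned assessments, the highest grade (maximum severity) across all sources will be used". Under section 2.2, reactogenicity data are completely missing when "all 7 days of e-diary collection were missing and no reactogenicity events were reported on the participant-reported reactogenicity CRF". Section 5.3 treats a missing day in a partly completed diary as a day without events.

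The SAP for Substudies A and B is explicit in its own section 3.1.1.2: "any AEs recorded on the AE CRF that are considered systemic events starting within 7 days after vaccination will be consolidated with e-diary data".

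**The concern.** The surveillance sentence in Substudy C is the same one used for Substudies A and B (10.7.8.5.7 and 10.8.8.5.7). It works there because the A/B SAP goes to the AE page and collects the events. Substudy C reactogenicity relies instead on a separate reactogenicity form, and its SAP names that form where the A/B SAP names the AE CRF. The surveillance sentence was not brought into line. A site that follows it exactly therefore puts the symptom on a page that no written endpoint rule consults.

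At stake is the percentage of participants with each systemic event, which is a primary safety endpoint. The symptoms concerned are ones that the investigator has just judged more likely to come from the vaccine, so any error understates reactogenicity. It matters most for events that few participants report.

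**Working it through.** The plan states no figure on this point, so there is none to reproduce. The check sets the rules side by side, follows one participant through them, and bounds the effect.

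**1. Rules side by side**

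| Rule | Substudies A and B | Substudy C |
|---|---|---|
| Overlapping symptom, no positive test, not in diary | Recorded as an AE (protocol 10.7.8.5.7, 10.8.8.5.7) | Same instruction (10.9.8.5.8) |
| Event missed in the diary but told to the site | AE page (8.3.4) | No such instruction (8.3.5) |
| Confirmed Grade 4 event | Designated CRF and also an AE (8.3.4.2, 8.3.4.3) | CRF, page not named (8.3.5.2, 8.3.5.3) |
| AE-page events in the systemic-event endpoint | Consolidated with diary data (SAP 3.1.1.2) | No rule |
| Severity of those events | AE intensity grade (SAP 3.1.1.2) | No rule |
| AE-page fever without a temperature | Kept, temperature range shown as unknown (SAP 3.1.1.2) | No rule |
| CRF named when defining completely missing data | AE CRF (SAP 2.2, 4, 5.3) | Reactogenicity CRF (SAP 2.2, 4) |

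**2. One participant.** Suppose vomiting occurs on Day 3, the Day 3 diary is not completed, the other six days are answered no, the local test is negative, and the site records an AE.
- Table 6 of the Substudy C SAP, applied to systemic events through 3.1.1.2, codes a mix of no and missing as absent. Section 5.3 agrees. Unless the AE page is consulted, the result is no vomiting.
- If vomiting was entered on any other diary day, the participant is already counted and nothing changes.
- If the whole diary is blank and the reactogenicity CRF has no entry, the note to Table 6 leaves the participant out of the summary altogether.

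**3. Size per participant.** With x participants already counted among N, the shift is (x+1)/N − x/N = 1/N.
- Cohorts 1 and 2 combined, N=200: 1/200 = 0.5 point.
- Cohort 3, N=100: 1/100 = 1.0 point; in each of its age groups, N=50: 1/50 = 2.0 points.
- Ages 12–17 in Cohort 2, at the maximum N=20: 1/20 = 5.0 points.

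For a participant left out altogether, the Cohort 3 difference is (x+1)/100 − x/99 = (99 − x)/9,900. This is at most 99/9,900 = 1.0 point, so the same ceiling applies.

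For m such participants the ceiling is m/N. The documents give no value of m. Taking m from 1 to 5 as an assumption, the range is 0.5 to 2.5 points for N=200 and 1 to 5 points for N=100.

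**4. A rare event.** Clopper-Pearson 95% intervals:
- 0/100: 0 to 3.62%; 1/100: 0.03 to 5.45%.
- 0/200: 0 to 1.83%; 1/200: 0.01 to 2.75%.

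One recovered case visibly changes the reported line for an uncommon event.

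**The case against.** The strongest reply is that the Substudy C SAP does not exclude the AE page. Its source wording, e-diary and/or CRF, names no page, the AE section is part of the CRF, and the multi-source list is only an example. A reader might infer that these events certainly drop out of the endpoint; the documents do not say so. That part of the reply stands. It does not close the gap, though. The main analysis (SAP 6.1.1.2.1) reports by maximum severity, and fever is grouped by temperature. On the broad reading, the SAP still does not say which AE terms count, how AE intensity becomes a severity grade, or where a fever without a temperature goes.

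The route is also narrow: one of five symptoms, within 7 days, judged reactogenic, without a positive test, and not in the diary. Staff also review the diary at Visits C2 and C3, and at C4 for Cohort 2, and record their assessment in the CRF. This lowers the likely number of cases. It does not say what happens to an event once it is on the AE page.

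A reader might further infer that comparisons of reactogenicity between substudies are distorted. None is planned: Substudy A is a control for immunogenicity only, and Substudy C is descriptive throughout.

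**Conclusion.** The point holds as a mismatch between a recording instruction and the analysis rule for a primary safety endpoint. On the likely reading, a participant whose symptom reached only the AE page is coded as having no such event. The ceiling is 0.5 point per participant in Cohorts 1 and 2 combined and 1 point in Cohort 3, with larger ceilings in the age subgroups.

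This rests on planned sample sizes, on the AE page not being consulted, and on the symptom not being entered on another diary day. The number of affected participants is unknown.

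Two stronger readings are not supported. The events are not lost to safety reporting, since they count in the primary AE endpoint (SAP 6.1.1.3). Nor does each one add a matching amount to the AE percentage: that rises only if the participant has no other AE. The problem is modest, but cheap to remove and best settled in writing, because sponsor staff are largely unblinded (protocol 10.9.6.4.3).

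**What to change.** 1. In protocol 10.9.8.5.8, replace the AE alternative with the reactogenicity CRF that the Substudy C SAP uses. The protocol does not use that form's name, so first confirm that the form accepts these entries outside unplanned assessments.
2. For data already on the AE page, add the A/B rule to Substudy C SAP 3.1.1.2. AE-page events considered systemic events, with onset in Days 1–7, are consolidated with diary data and graded by AE intensity. A fever without a temperature is shown in an unknown range.
3. Make the matching edit to the definition of completely missing data in Substudy C SAP sections 2.2 and 4, so that such an AE-page entry counts as data.
4. Leave these events in the AE percentage. The A/B SAP adds them to the reactogenicity summary and states no removal from the AE tables.

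The cost is one protocol phrase, a few SAP sentences and minor programming, with the A/B text as precedent.
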